6.3 Sample Size

For each assay, PPA and NPA³⁵ will be estimated for each of three diagnostic tests defined by pathogen - anatomical site combinations:

- *Neisseria gonorrhoeae* in the rectum
- *Neisseria gonorrhoeae* in the pharynx
- *Chlamydia trachomatis* in the rectum
- *Chlamydia trachomatis* in the pharynx

Each pathogen/anatomic site combination will be evaluated by constructing 95% Score confidence interval estimates for PPA and NPA and evaluating whether 90% can be ruled out by the lower bound of the CI with reasonable confidence.

NPA is expected to be greater than PPA and there will be considerably more not-infected than infected anatomic site, implying that there will be greater power for evaluating NPA. Thus it will suffice to size the study to evaluate PPA.

Assuming that the true PPA is 96%,¹³ then 157, 174, and 196 evaluable participants that are infected are needed to have 80%, 85%, and 90% power respectively to demonstrate a PPA of greater than 90%. Since all of the participants will contribute to the evaluation of all three pathogen-anatomical site diagnostic tests, it will suffice to size the study for the diagnostic test with the lowest expected prevalence (except CT in the pharynx). The study will be more than sufficiently sized for more prevalent disease.

It is expected that the disease prevalence of NG in the rectum, NG in the pharynx, and CT in the rectum will each be greater than 7.5% in the population under evaluation.^{13,14,16-20} Table 3 summarizes the required number of participants to have 80% and 90% probabilities of obtaining the 157, 174, and 196 evaluable participants that are disease-positive to have 80%, 85%, and 90% power when the true prevalence of disease is 7.5%, 10%, and 12.5%.

Table 3: Sample size required number to have 80% and 90% probabilities of obtaining the 157, 174, and 196 evaluable participants that are disease-positive when the true prevalence of disease is 7.5%, 10%, and 12.5% in order to have 80%, 85%, and 90% power (two-sided alpha=0.05) to conclude that sensitivity is greater than 90% when the true sensitivity is 96%.

| Prevalence of Disease Positive | Power | Required Disease Positive to Obtain Power | Required Sample Size to have 80% probability of obtaining required Disease positive participants | Required Sample Size to have 90% probability of obtaining required Disease positive participants |
|--------------------------------|-------|---|--|--|
| 7.5% | 80% | 157 | 2250 | 2325 |

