СТ	Chlamydia trachomatis
DCRI	Duke Clinical Research Institute
DNA	Deoxyribonucleic acid
FDA	Food and Drug Administration
HIV	Human immunodeficiency virus
ICMJE	International Committee of Medical Journal Editors
ID	Identification
IFU	Instructions for Use
IRB	Institutional Review Board
ISRC	Independent Study Review Committee
LGBT	Lesbian, gay, bisexual and transgender
NAAT	Nucleic acid amplification test
NR	This means no test was run and there is no result
NPA	Negative percent agreement
NPV	Negative predictive value
NG	Neisseria gonorrhoeae
NIH	National Institutes of Health
OHRP	Office of Human Research Protections
PPA	Positive percent agreement
PPV	Positive predictive value
PI	Principal Investigator
RNA	Ribonucleic acid
rRNA	Ribosomal ribonucleic acid
SDMC	Statistical and Data Monitoring Center
STD	Sexually transmitted diseases
WHO	World Health Organization

STUDY SCHEMA AND OBJECTIVES

- DESIGN A cross-sectional, single visit study to evaluate the diagnostic accuracy of three nucleic acid amplification tests (NAATs) for detection of *Neisseria gonorrhoeae* and *Chlamydia trachomatis* from a set of four swabs each collected from both the pharyngeal and rectal sites, respectively.
- DURATION This is a single visit study. It is estimated that the study will take between 6 and 12 months after enrollment of the first participant to fully enroll.

Note: Study duration was updated to 12 to 24 months during the study.

SAMPLE SIZE Up to 2,500 participants

Note: Sample size was increased to up to 3000 participants per recommended changes by the independent statistician during the study.

POPULATION Symptomatic or asymptomatic male, female, or transgender participants:

- Who are patients attending a participating clinic for evaluation of sexually transmitted disease (STD), and
- \circ ≥18 years of age at date of screening, and
- Able and willing to provide informed consent, and
- Willing to comply with study procedures, including collection of 4 swabs each from the pharynx and rectum for NG and CT testing.

NUMBER OF SITES Up to 10

STRATIFICATION Randomization of the swab order will not be stratified. Swabs will be collected from all participants at each extragenital site.

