5.3. Interim Analysis

5.3.1. Interim Analysis Considerations

The study cannot be stopped at the interim for reaching regulatory goals in order to preserve error rates / coverage probability and to ensure enough data for subgroup analyses. Since the trial cannot be stopped for attainment of the regulatory goal, no adjustment to confidence levels are necessary.

Although it is anticipated that swab collection and data completeness will be high for both anatomical sites, both the Intention-to-Diagnose (ITD) and modified Intention-to-Diagnose (mITD) infection rates⁷, as described in **Table 5**, will be estimated. It is expected that disease prevalence (infection rate) of NG in the rectum, NG in the pharynx, and CT in the rectum will each be greater than 7.5% in the population under evaluation. Disease prevalence of CT in the pharynx is expected to be rare.

Table 5: Infection rate calculation for each test under consideration

Intent-to-Diagnose (ITD) Infection Rate	Number of infected ASIS results for test under consideration / Total number of ASIS results ¹
Modified Intent-to-Diagnose (mITD) Infection Rate	Number of infected ASIS results for test under consideration / Total number of ASIS results with exclusion of invalid results ²
	I infected, not infected, indeterminate and invalid ASIS results. I infected, not infected, and indeterminate ASIS results.

Operationally, a range of scenarios for the unobserved data will be generated at each interim review to assist with the decision making regarding sample size adjustments. To ensure enough infected participants to estimate PPAs with desired precision, the lowest ITD/mITD infection rate across the three assays and the three organism/site combinations (except CT in the pharynx) will be used as the observed rate for interim analysis. Of note, it is assumed that there will be greater precision to evaluate NPA as it is expected that there will be more not-infected results than infected results for each anatomic site.

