Table 6 and **Table 7** illustrate hypothetical scenarios when the observed infection rate after the first 1000 participants is rarer than anticipated (equal to 5%, **Table 6**) or more prevalent than anticipated (equal to 10%, **Table 7**), respectively. For both tables, a range of infection rates for the unobserved data (scenarios A-C) are also presented to demonstrate the probability and corresponding total sample sizes to obtain 150, 175 or 200 disease positive participants, respectively, at the end of study.

If infection is rarer than anticipated, then increases to sample size may be considered as demonstrated in scenario A from Table 6. In this case, should the observed prevalence of 5% remain unchanged for the unobserved data, then enrollment of approximately 3200 total participants would be needed to ensure at least 80% probability of obtaining 150 disease positive participants. However, should the infection rate increase to 9% (Scenario C, **Table** 6), then sample size adjustments may not be warranted.

Alternatively, if infection is more prevalent than expected, a smaller sample size may be considered as demonstrated in scenarios A and B from **Table 7**.

⁷ Fundamental Concepts for New Clinical Trialists. A Evans, S. and A Ting, N. 9781420090871. https://books.google.com/books?id=G1IUPQAACAAJ. 2015. Taylor & Francis.

Sample size adjustments may also be considered if there is evidence that the number of ASIS results categorized as invalid will impact study accrual time and/or data analyses.

Table 6: Hypothetical illustration of simulated infection rates after first 1000 participants and observed prevalence
of 5%

Observed R	Brova	lence of						
TD infectio ate at	n	Disease Positive (%) 5%		sitive (N)				
nterim				pants				
Example Sc	cenarios for Un	observed Dat	a					
	Assumed		Es	Estimated probability (P) and sample size (N) to obtain:				
Scenario	prevalence rate ¹	prevalence rate ²	150 Disease+ total participants		175 Disease+ total participants		200 Disease+ total participants	
			Р	Ν	Р	N	Р	Ν
			<50%	2500	<50%	2500	<50%	2500
Α	5%	5%	80%	3220	80%	3740	80%	4260
			90%	3340	90%	3860	90%	4380
_			64%	2500	<50%	2500	<50%	2500
В	7%	6.2%-6.4%	80%	2589	80%	2956	80%	3323
			90%	2669	90%	3046	90%	3413
			800/	2232	76%	2500	<500/	2500
С	0%	7 20/ 7 60/	80%	-		2500	<50%	2500
L L	9%	7.2%-7.6%	90%	2302	80%	2519	80%	2807
bserved an	ed prevalence r ad assumed prev	alence rates f	or the entire du	ration of study	for a given sa	ample size.	-	the

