+	+	Not indicated	Infected	XX
+	-	+	Infected	XX
(Remaining observed combination	ns as described in Table 4 .)		
Anatomical Site and Organism	n: CT, throat			
Comparator NAAT Result 1	Comparator NAAT Result 2	Tiebreaker NAAT result	ASIS	Frequency (n)
+	+	Not indicated	Infected	XX
+	-	+	Infected	XX
(Remaining observed combinations as described in Table 4 .)				

c. Table/Figure: Number (%) of observed total test results, ASIS results, and prevalence (i.e., infection) rate. This will be conducted for each test under consideration and be presented by anatomical site and organism combination as shown in **Table 10** below. [Data source: LAB DATA]

Table 10: Number (%) of observed total test results, ASIS results, and prevalence (i.e., infection) rate for each test under consideration by anatomical site and organism

Test under con	Test under consideration: Company 1 System							
	Comparator NAATs: Company 2 and Company 3 Systems							
Tiebreaker NA	AT: Tiebre	aker Syster	m					
	Sample	Size (N)		AS	SIS		Prevalence	
	N	. ,					(P,	%) P
	(ITD)	N (mITD)	Infected	Not infected	Indeterminate	Invalid	(ITD)	(mITD)
NG, rectum								
NG, throat								
CT, rectum								
CT, throat								
Test under con								
			d Company 3 Sy	rstems				
Tiebreaker NA	AT: Tiebre	aker Systei	m					
	Sample	Size (N)		AS	SIS		Prevalence (P, %)	
	N (ITD)	N (mITD)	Infected	Not infected	Indeterminate	Invalid	P (ITD)	P (mITD)
NG, rectum								
NG, throat								
CT, rectum								
CT, throat								
Test under con								
			d Company 2 Sy	vstems				
Tiebreaker NA	AT: Tiebre	aker Syste	m					
	Sample	Size (N)	ASIS			Preva (P,	llence %)	
	N (ITD)	N (mITD)	Infected	Not infected	Indeterminate	Invalid	P (ITD)	P (mITD)
NG, rectum								
NG, throat								
CT, rectum								
CT, throat								

- a. Table/Figure: Predicted infection rate summary for range of scenarios (see **Table 6** and **Table 7** described in Section 5.3.1).
- b. Table: Observed frequency of tiebreaker run versus expected number of runs (number, %).

c. Table: Using Fischer's exact test, the association between of test results and randomized swab order will be examined. Associations will be conducted by anatomical site and organism combination.

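### The SAP's interim sample-size tables aim for as few as 150 infected participants, below the protocol's minimum of 157, and their printed probabilities do not condition on the infections already observed

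*SAP*

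**What the plan says.** Protocol Section 6.3 states that "157, 174, and 196 evaluable participants that are infected are needed to have 80%, 85%, and 90% power respectively" to show a PPA above 90% when the true value is 96%.

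SAP Section 5.3.1 covers the interim checks of the infection rate. It says that "a range of scenarios for the unobserved data will be generated at each interim review to assist with the decision making" on sample size. Tables 6 and 7 illustrate this for an interim after 1,000 participants with an observed rate of 5% or 10%, and the text describes their purpose as "to demonstrate the probability and corresponding total sample sizes to obtain 150, 175 or 200 disease positive participants". For Table 6 Scenario A (rate staying at 5%) it concludes: "then enrollment of approximately 3200 total participants would be needed to ensure at least 80% probability of obtaining 150 disease positive participants". It also says that "if infection is more prevalent than expected, a smaller sample size may be considered as demonstrated in scenarios A and B from" Table 7.

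SAP Section 5.3.2 lists among the interim outputs a "Predicted infection rate summary for range of scenarios" and points back to Tables 6 and 7. The Sample Size entry of the SAP's study schema, which first gives a ceiling of 2,500, notes: "Sample size was increased to up to 3000 participants per recommended changes by the independent statistician during the study".

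The SAP gives no reason for replacing 157, 174 and 196 by 150, 175 and 200, and no formula for the probabilities.

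**The concern.** There are two separate problems.

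First, 150 is below the smallest infected count that the protocol accepts. The other two targets slightly exceed their counterparts (175 against 174, 200 against 196), so only the lowest column is short. It is also the column behind the one worked sentence.

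Second, once 1,000 participants have been observed, their infected count is known (50 in Table 6, 100 in Table 7). Only later participants are uncertain. A projection that treats the first 1,000 as random again answers a different question.

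These tables are the template for the summary that the independent statistician receives at each review, and that review can move enrolment either way. If enrolment stopped at a size read from the lowest column, the trial could finish short of the infected count that its power statement needs.

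**Working it through.** **Inputs.** Protocol 6.3: null PPA 0.90, true PPA 0.96, two-sided alpha 0.05, targets 157/174/196. SAP 5.3.1: targets 150/175/200; first 1,000 participants with 50 infected (Table 6) or 100 (Table 7); assumed later rates of 5%, 7% and 9% for Table 6 Scenarios A, B and C, and 10% for Table 7 Scenario A. Table 7 Scenarios B and C are too broken in the available text to rely on.

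**Step 1: the protocol's targets.** The normal formula is

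n = [1.96 × √(0.90 × 0.10) + z(power) × √(0.96 × 0.04)]² / 0.06².

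It gives 157.5, 173.8 and 195.6 for 80%, 85% and 90% power, which agrees with 157, 174 and 196. Solved for power, it gives 77.3% at 150, 79.8% at 157, 85.3% at 175 and 90.8% at 200.

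**Step 2: how the printed probabilities arise.** Let T be the target, N the total enrolled, x the infected count among the first 1,000, and p the later rate. Three calculations were compared:

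- first 1,000 redrawn as Bin(1000, observed rate), total strictly greater than T;
- x fixed, total strictly greater than T;
- x fixed, total at least T, that is P[Bin(N − 1000, p) ≥ T − x].

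| Cell | Printed | Redrawn, > T | Fixed, > T | Fixed, ≥ T |
|---|---|---|---|---|
| Table 6 B, 150, N = 2500 | 64% | 64.2% | 67.1% | 70.8% |
| Table 6 C, 175, N = 2500 | 76% | 76.5% | 80.3% | 82.8% |
| Table 6 A, 150, N = 3220 | 80% | 80.1% | 84.7% | 87.0% |
| Table 7 A, 150, N = 1610 | 80% | 80.8% | 92.5% | 94.3% |

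The first two rows discriminate best, because their N is fixed at 2,500 and not chosen to reach a round probability. They match the redrawn calculation and neither conditional one. In Table 6 B, about 3.0 points of the gap come from redrawing and 3.6 from the strict inequality. In Table 7 A the split is about 11.7 and 1.8.

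**Step 3: effect on N for the SAP's own targets.** The smallest N with x fixed and at least T infected, for an 80%/90% chance of 150, is 3162/3254 (Table 6 A), 2543/2608 (B), 2199/2249 (C) and 1555/1588 (Table 7 A). The printed sizes are 3220/3340, 2589/2669, 2232/2302 and 1610/1670. Over all readable targets the printed N is 1.2% to 2.6% too large in Table 6 and 2.5% to 5.2% too large in Table 7 Scenario A. In Table 6 C, 2,487 participants suffice for an 80% chance of 175, so the planned 2,500 already meets it where the table prints 76%.

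**Step 4: chance of reaching 157 at the printed sizes for 150.** Using P[Bin(N − 1000, p) ≥ 157 − x]:

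| Scenario | At the size listed for 80% | At the size listed for 90% |
|---|---|---|
| Table 6 A | 66.5% (3220) | 84.0% (3340) |
| Table 6 B | 67.5% (2589) | 83.9% (2669) |
| Table 6 C | 66.5% (2232) | 85.0% (2302) |
| Table 7 A | 72.4% (1610) | 91.4% (1670) |

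At N = 2,500 in Table 6 B the chance of 157 is 43%, where the table shows 64% for 150. At the present ceiling of 3,000 under Table 6 A it is 25%, against 51% for 150.

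**Step 5: both faults corrected.** Total N for an 80%/90% chance:

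| Target | Table 6 A | Table 6 B | Table 6 C | Table 7 A |
|---|---|---|---|---|
| 157 | 3308/3402 | 2647/2714 | 2280/2331 | 1629/1664 |
| 174 | 3661/3762 | 2899/2971 | 2476/2531 | 1808/1846 |
| 196 | 4116/4226 | 3224/3302 | 2729/2788 | 2037/2081 |

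**The case against.** The best defence is that the tables are labelled hypothetical, use round numbers, and nowhere claim that 150 gives 80% power. A smaller sample is only something that may be considered, on the advice of an independent statistician who sees three targets side by side. A reader who took the 175 column would be safe: at 1,870 in Table 7 Scenario A the chance of 157 is above 99.9%. The probability error is conservative, and the net correction at the lowest target is small. No enrolment decision is shown to have been wrong, and the ceiling was in fact raised. Nor is 157 a sharp boundary: the normal formula puts it at 79.8%.

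Much of this stands and limits the seriousness. It does not remove the point. The SAP has the same summary produced at each review with explicit reference to these tables, so the low target and the method carry over. The power argument also cuts the other way: an exact calculation with the Score interval gives 74.7% power at 150 and 82.1% at 157.

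The caution about method is fair. That the printed figures are not conditional is well supported, because neither conditional version fits. The strict inequality is less certain: the sentence about 3,200 participants also agrees with an unconditional calculation requiring at least 150, whose minimum is 3,199.

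**Conclusion.** The concern holds on both parts. The lowest interim target is 7 infected participants below the protocol's minimum (157 − 150) and corresponds to 77.3% power. The printed probabilities do not condition on the observed count, whatever code produced them.

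The low target is the unsafe part: at the sizes listed for an 80% chance, the chance of reaching 157 is 66% to 68% in Table 6 and 72% in Table 7 Scenario A. The probability fault is conservative. The two partly offset at the lowest target; at 175 and 200 the sample size is simply overstated. The sentence about 3,200 participants is true for 150, but 150 is not enough. The suggestion that Table 6 Scenario C may need no increase survives, with a 99.6% chance of 157 at 2,500.

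These results assume that later participants are independent with exactly the stated rate, and the 25% and 43% figures belong to illustrative scenarios, not to observed data. The documents do not say which target lay behind the increase to 3,000. The final PPA and NPA calculations are unaffected. This should be corrected because the tables inform sample-size decisions, though the net change in N is modest.

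**What to change.** In SAP Section 5.3.1, replace the targets by 157, 174 and 196. State the formula: the probability that a binomial count, with N minus the number already observed as its size and the assumed later rate as its probability, is at least the target minus the infections already observed. Reissue Tables 6 and 7 on that basis, using the Step 5 values for Table 6 and Table 7 Scenario A. The sponsor should recompute Table 7 Scenarios B and C from the source. Restate the worked sentence as about 3,300 participants for an 80% chance of 157, and use the same formula for the interim summary in Section 5.3.2.

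The cost is SAP wording and a short re-run, with no change to design or conduct. At the lowest target the 80% size moves from 3,220 to 3,308 in Table 6 Scenario A (88/3220 = 2.7%) and from 1,610 to 1,629 in Table 7 Scenario A (19/1610 = 1.2%).

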5.3.2. Interim Analyses

Note: Analysis programs will require independent results verification per CBAR PROG.10033.

a. Table: For each diagnostic assay, frequency of observed test outcomes by anatomical site and organism combination as shown in **Table 8**. [Data source: LAB DATA]

Note: Test results for each diagnostic assay were defined previously in Section 5.1.

Table 8: Frequency of observed test outcomes by anatomical site and organism combination

NAAT: Company 1 system Test Results							
	Not detected	Detected	Invalid	Error	No result		
NG, rectum							
NG, throat							
CT, rectum							
CT, throat							
NAAT: Company	/ 2 system Test Res	ults					
	Negative	Positive	Equivocal	Invalid			
NG, rectum							
NG, throat							
CT, rectum							
CT, throat							
NAAT: Company	/ 3 system Test Res	ults					
	Negative	Positive					
NG, rectum							
NG, throat							
	Negative	Positive	Equivocal				
CT, rectum							
CT, throat							
NAAT: Tiebreak	er system Test Resu	llts					
	Negative	Positive	Equivocal	Invalid			
NG, rectum							
NG, throat							
CT, rectum							
CT, throat							

b. Table/Figure: Frequency of comparator NAAT result and tiebreaker result combinations to define ASIS as shown in Table 9. This will be conducted for each test under consideration and be presented by anatomical site and organism combination. There will be a total of three tables to reflect the three tests under consideration. [Data source: LAB DATA]

Note: Only combinations with a frequency of one or greater will be shown. Any combination not shown will indicate that this combination was not observed (i.e., frequency equal to 0).

 Table 9: Frequency of comparator NAAT result and tiebreaker result combinations by anatomical site and organism for test under consideration XX

Test Under Consideration: XXX				
Anatomical Site and Organisi	n: NG, rectum			
Comparator NAAT Result 1	Comparator NAAT Result 2	Tiebreaker NAAT result	ASIS	Frequency (n)
+	+	Not indicated	Infected	XX
+	-	+	Infected	XX
	(Remaining observed combination	is as described in Table 4.)		
Anatomical Site and Organisi	n: NG, throat			
Comparator NAAT Result 1	Comparator NAAT Result 2	Tiebreaker NAAT result	ASIS	Frequency (n)
+	+	Not indicated	Infected	XX
+	-	+	Infected	XX
(Remaining observed combinations as described in Table 4 .)				
Anatomical Site and Organism: CT, rectum				

Comparator NAAT Result 1	Comparator NAAT Result 2	Tiebreaker NAAT result	ASIS	Frequency (n)
+	+	Not indicated	Infected	XX
+	-	+	Infected	XX
(Remaining observed combination	ns as described in Table 4 .)		
Anatomical Site and Organism	n: CT, throat			
Comparator NAAT Result 1	Comparator NAAT Result 2	Tiebreaker NAAT result	ASIS	Frequency (n)
+	+	Not indicated	Infected	XX
+	-	+	Infected	XX
(Remaining observed combinations as described in Table 4 .)				

c. Table/Figure: Number (%) of observed total test results, ASIS results, and prevalence (i.e., infection) rate. This will be conducted for each test under consideration and be presented by anatomical site and organism combination as shown in **Table 10** below. [Data source: LAB DATA]

Table 10: Number (%) of observed total test results, ASIS results, and prevalence (i.e., infection) rate for each test under consideration by anatomical site and organism

Test under con	Test under consideration: Company 1 System							
	Comparator NAATs: Company 2 and Company 3 Systems							
Tiebreaker NA	AT: Tiebre	aker Syster	m					
	Sample	Size (N)		AS	SIS		Prevalence	
	N	. ,					(P,	%) P
	(ITD)	N (mITD)	Infected	Not infected	Indeterminate	Invalid	(ITD)	(mITD)
NG, rectum								
NG, throat								
CT, rectum								
CT, throat								
Test under con								
			d Company 3 Sy	rstems				
Tiebreaker NA	AT: Tiebre	aker Systei	m					
	Sample	Size (N)		AS	SIS		Prevalence (P, %)	
	N (ITD)	N (mITD)	Infected	Not infected	Indeterminate	Invalid	P (ITD)	P (mITD)
NG, rectum								
NG, throat								
CT, rectum								
CT, throat								
Test under con								
			d Company 2 Sy	vstems				
Tiebreaker NA	AT: Tiebre	aker Syste	m					
	Sample	Size (N)	ASIS			Preva (P,	llence %)	
	N (ITD)	N (mITD)	Infected	Not infected	Indeterminate	Invalid	P (ITD)	P (mITD)
NG, rectum								
NG, throat								
CT, rectum								
CT, throat								

- a. Table/Figure: Predicted infection rate summary for range of scenarios (see **Table 6** and **Table 7** described in Section 5.3.1).
- b. Table: Observed frequency of tiebreaker run versus expected number of runs (number, %).

c. Table: Using Fischer's exact test, the association between of test results and randomized swab order will be examined. Associations will be conducted by anatomical site and organism combination.

